6 ANALYSIS POPULATIONS

6.1 FULL ANALYSIS SET (FAS)

The FAS population will consist of all Stage II treated subjects. This population will be utilized as a primary analysis population for the primary and secondary performance endpoints and exploratory endpoints.

6.2 PER-PROTOCOL POPULATION (PP)

The PP population will consist of FAS subjects who do not have major protocol deviations with data analyzed according to treatment received. This population will be utilized as a secondary analysis population for the primary and secondary performance endpoints and exploratory endpoints. Major protocol violations are described in Section 7.4.

6.3 SAFETY POPULATION

The Safety analysis population will consist of Stage I and Stage II treated subjects. This population will be utilized as the primary analysis population for the safety analyses. Summaries will be presented by study stage and overall.

7 GENERAL ISSUES FOR STATISTICAL ANALYSIS

The study will use a frequentist approach to statistical analysis. Descriptive statistics (mean, standard deviation, frequencies, etc.) for baseline participant characteristics, patient disposition and other relevant study parameters will be reported.

7.1 ANALYSIS SOFTWARE

Analysis data sets, statistical analyses and associated output generated by Avania will be generated using SAS® Software version 9.4 or later.

7.2 DISPOSITION OF SUBJECTS AND WITHDRAWALS

The data collected up to the time point the subject has withdrawn or discontinued will be included as part of the clinical investigation. The number and percent of subjects in each analysis population will be presented. All subjects who provide written informed consent will be accounted for.

The frequency and percent of subjects who completed each scheduled assessment will be presented in a table for the FAS population. The number and percentage of FAS patients prematurely withdrawing will be presented overall and by reason of discontinuation.

7.3 METHODS FOR WITHDRAWALS AND MISSING DATA

Reasonable efforts will be made to obtain complete data for all subjects; however, missing observations may occur due to subjects lost to follow-up or noncompliance with required assessments. Reasons for

missing visits and assessments will be captured in data collection forms as a protocol deviation or as a subject exit/termination. Any missing data on study endpoints will be described in the CSR.

The primary analysis of the primary performance endpoint will be on the FAS population with available data.

For the primary performance endpoint regarding achieving hemostasis at 3 minutes, a "tipping point" sensitivity analysis will be used to assess the effect of missing data on the results of the hypothesis testing of the primary endpoint. I.e., for the primary endpoint, if the null hypothesis is rejected on the FAS population with available data, then FAS patients who are missing will be imputed as a failure, one at a time cumulatively, and the null hypothesis will be tested after each cumulative imputation until the "tipping point" is reached (i.e., until the null hypothesis is no longer rejected).

Data will be analyzed as available, with no imputation of missing data for other endpoints.

7.4 PROTOCOL DEVIATIONS

Protocol deviations will be summarized in a summary table. This summary will include the number and percent of subjects (overall and by site) with each deviation type. A listing will be generated as well.

In this study, deviations from the clinical investigation plan to the in/exclusion criteria and deviations that affect the primary endpoints are considered major deviations. Deviations that may affect the secondary endpoints are considered minor deviations. All deviations will be reviewed by the medical monitor. The medical monitor is responsible for major/minor classification of the deviations.

7.5 MULTIPLE COMPARISONS AND MULTIPLICITY

The interim analysis of the primary performance endpoint will be performed once approximately 69% (n≈25) of the planned evaluable Stage II subjects are treated. To account for multiple testing and control the overall Type I error rate of the study at one-sided 0.025 level, a group-sequential design will be used based on the Lan-DeMets approach with an O'Brien-Fleming alpha-spending function. The impact of the interim analysis on the type I error is in Section 9.1.

7.6 ASSESSMENT OF HOMOGENEITY

This clinical investigation will be conducted in the Netherlands and up to 7 sites will participate in this study. A test of homogeneity across sites will be done to determine if the study sites have reasonably homogeneous responses for the primary endpoint.

Logistic regression, with the primary endpoint, achieving hemostasis at 3 min (yes/no) as the dependent variable and investigational site as the independent variable, will be used to assess homogeneity across sites on the FAS population.

It is expected that a comparable number of subjects is enrolled and treated at each investigational site. There is no minimum or maximum number of subjects to be enrolled or treated by each site, in stage II,

however distribution between participating sites is monitored during the enrolment period. Low enrolling sites will be pooled for the homogeneity analysis. Study sites with fewer than 5 subjects may be combined into pseudosites. All pseudosite categorizations will be determined before the database is locked.

The association between investigational site and the primary performance outcome will be assessed at the 0.15 significance level. If the responses are not homogenous, an appropriate regression analysis will be done to determine if the lack of homogeneity is due to the site or due to a possible imbalance in baseline characteristics of the subjects across study sites. If the site effect is no longer significant at a 0.15 level of significance after adding the potentially unbalanced baseline covariates, then site will not be considered a source of lack of homogeneity.

7.7 TIMING OF ASSESSMENTS AND EVENTS FOR ANALYSIS

Study day 0 is the date of the index procedure. Study days will be calculated as follows:

• Study Day = Event Date – Surgery Date

All the primary and secondary endpoints are collected at the treatment day. Safety endpoints are collected at the treatment, post-surgery, and 6 weeks (+/- 2 weeks) follow-up visit. Some subjects may have an additional phone consultation at 2-6 weeks post-procedure for the assessment of safety during Stage I of the clinical investigation. This visit will include assessment of adverse events and will only take place for subjects in Stage I of the clinical investigation who did not complete the 6 weeks follow-up visit.

8 DEMOGRAPHICS AND OTHER BASELINE CHARACTERISTICS

Safety and FAS populations will be utilized for the analyses discussed in this section. When summarizing data, continuous variables will be summarized with number of subjects, mean, standard deviation, median, quartiles, minimum, and maximum, while categorical variables will be summarized with frequency and percentage.

8.1 DEMOGRAPHICS AND PHYSICAL EXAM

Subject's demographics and physical examination such as age, weight, heart rate and other continuous variables will be summarized by reporting number of observations, mean, standard deviation, median, quartiles, minimum, and maximum. Sex, race, and disease diagnosis will be summarized with frequency and percentage.

8.2 PRIOR AND CONCURRENT MEDICATIONS

All relevant prior and concurrent medications will be presented in a listing with medication name, route of administration, dose, and other data captured on the eCRF.

8.3 BASELINE MEDICAL HISTORY

The subject's relevant medical history and allergies will be recorded on the eCRF and presented in a summary table by frequency and percentage of subjects.

8.4 BASELINE LABS

Tables presenting descriptive statistics (N, mean, standard deviation, median, quartiles, minimum, maximum) of laboratory values will be presented. The laboratory values include hematology tests (hemoglobin (Hb), thrombocytes), coagulation tests (prothrombin time (PTT), activated partial thromboplastin time (aPTT), international normalized ratio (INR)), chemistry tests (bilirubin level, calcium, potassium, sodium, chloride, albumin, AST, ALT). Whether or not laboratory values are normal or out of range of expected value will also be summarized by frequency and percentage.

9 PERFORMANCE ANALYSES

9.1 PRIMARY ENDPOINT ANALYSIS

The primary performance endpoint is the percentage of patients achieving hemostasis at 3 minutes using GATT-Patch.

The statistical null (H₀) and alternative (H₁) hypotheses are the following:

H₀: p_{GATT} ≤ 65.4%

H₁: p_{GATT} > 65.4%

where p_{GATT} is the percentage of patients achieving hemostasis at 3 minutes using GATT-Patch and 65.4% is the performance goal (PG) to demonstrate non-inferiority of GATT-Patch compared to current knowledge (literature-based) of standard of care.

The null hypothesis (H₀) for this endpoint states that the true proportion of subjects treated with the GATT-Patch who achieve the primary performance endpoint is no higher than 65.4%. The alternative hypothesis the GATT-Patch trial aims to demonstrate is that the true proportion of subjects who achieve non-inferiority greater than 65.4%.

The interim analysis of the primary performance endpoint will be performed once approximately 69% ($n\approx 25$) of the planned evaluable Stage II subjects are treated. To account for multiple testing and control the overall Type I error rate of the study at one-sided 0.025 level, a group-sequential design will be used based on the Lan-DeMets approach with an O'Brien-Fleming alpha-spending function. Based on this method, a test to demonstrate that the percentage of patients achieving hemostasis at 3 minutes using GATT-Patch is significantly greater than 65.4% will be performed at the interim review using the continuity corrected Z-test of proportion at a one-sided 0.0070 significance level. If the statistical analysis of the primary endpoint at the interim review yields a one-sided p-value less than 0.0070, then

the DMC may recommend stopping the trial for overwhelming successful performance. If the one-sided p-value is not less than 0.0070, then the study will continue and a final analysis to demonstrate that the percentage of patients achieving hemostasis at 3 minutes using GATT-Patch is significantly greater than 65.4% will be performed using the continuity corrected Z-test of proportion at the one-sided 0.0229 significance level. A sample size increase based on the Mehta-Pocock Promising Zone approach will not require an additional penalty to the final significance (alpha) level.

The primary analysis of the primary performance endpoint will be on the FAS with available data. The primary performance endpoint will also be analyzed on the PP population as a secondary analysis. If there are multiple appropriate bleeding sites for one patient, the first encountered bleeding site that requires topical hemostat application (primary bleeding site) will be considered for the analysis of the primary endpoint.

The number and percentage of patients achieving hemostasis at 3 minutes using GATT-Patch will be reported, including the confidence interval (CI) of the percentage based on Wilson's method with continuity correction and the one-sided p-value from the continuity corrected Z-test of proportion. In order to correspond with the significance levels that will be used at the interim and final analyses, a two-sided 98.6% CI will be calculated for the interim analysis and 95.42% CI will be calculated for the final analysis.

9.2 SECONDARY ENDPOINT ANALYSIS

The secondary performance endpoints will be determined using the FAS and PP population. The secondary endpoint analysis will be performed on the primary bleeding site. If there are multiple appropriate bleeding sites for one patient, this analysis will also be performed on all eligible bleeding sites that require topical hemostat application including the primary bleeding site.

The number of observations, mean, standard deviation, median, quartiles, minimum, and maximum time to hemostasis (seconds) will be presented, including the 95% CI of the mean. To account for the correlation within patient, when there are multiple bleeding sites available for one patient, the 95% CI will be estimated using a repeated measures linear regression model. An unstructured covariance matrix will be used. In the event that the model fails to converge, the compound symmetry covariance matrix will be used.

The number and percentage of bleeding sites achieving hemostasis at 30, 60, 90, 120, and 150 seconds, as well as the number and percentage of bleeding sites whichfail to reach hemostasis at 5 minutes will be presented. The 95% CI of the percentages based on Wilson's method with continuity correction will also be reported. To account for the correlation within patient, when there are multiple bleeding sites available for one patient, the 95% CI will be estimated using a repeated measures logistic regression model. An unstructured covariance matrix will be used. In the event that the model fails to converge, the compound symmetry covariance matrix will be used.

There will be no formal hypothesis testing on the secondary performance endpoints.

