4 SAMPLE SIZE

The plan is to enroll and treat the following number of subjects across two stages:

- Stage I: maximum of 12 subjects
- Stage II: 39 subjects (36 evaluable subjects, assuming 7.5% drop-out rate),

Therefore, the current plan is to treat a total of up to 51 (=12+39) subjects with GATT-Patch. A maximum of 153 replaceable subjects may be enrolled.

Note that the number of Stage II subjects may increase to a maximum of 61 treated subjects (56 evaluable subjects, assuming 7.5% drop-out rate) if a sample size increase is deemed necessary based on the interim sample size re-estimation. Therefore, the total sample size may increase to a maximum of 73 (=12+61) treated subjects based on the interim sample size re-estimation.

The sample size of Stage II is powered on the primary endpoint to allow for assessment of noninferiority of GATT-Patch compared to the current knowledge (literature-based) of standard of care regarding the percentage of subjects achieving hemostasis at 3 minutes.

Assuming the true percentage of subjects achieving hemostasis at 3 minutes using GATT-Patch is 89%, then an evaluable sample size of 36 evaluable subjects from Stage II achieves over 90% power to demonstrate non-inferiority of GATT-Patch compared to current (literature-based) knowledge of standard care (i.e., demonstrate that the percentage achieving hemostasis at 3 minutes for the population treated with GATT-Patch is significantly greater than the performance goal of 65.4%) using a one-sided continuity corrected Z-test of proportion. The sample size considers the interim analysis of the primary performance endpoint (performed when approximately 69% of the planned evaluable Stage II subjects are treated, i.e., n≈25 evaluable Stage II subjects) based on a group sequential design to allow for possible early stopping for overwhelming performance success. The Lan- DeMets approach with an O'Brien-Fleming alpha-spending function is used to control the overall Type I error rate of the study at a one-sided 0.025 level.

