If the study does not stop for overwhelming performance success at the interim review, then an unblinded conditional power calculation and sample size re-estimation will also be conducted at the interim review. The sample size re-estimation analysis will be performed by an independent statistician according to the Mehta-Pocock Promising Zone approach. The conditional power for demonstrating that the primary performance endpoint is significantly greater than performance goal of 65.4% will be calculated under the current protocol-specified evaluable sample size (n=36), under the assumption that the observed interim treatment effect (i.e., percentage achieving hemostasis at 3 minutes) is the true treatment effect size. If the conditional power under the protocol-specified evaluable sample size is between 39% to <90% (the promising zone), the evaluable sample size may increase to maintain conditional power of 90%. The sample size may increase to a maximum of 56 (i.e., 20 additional) evaluable subjects for Stage II. Such a sample size increase based on the Mehta-Pocock Promising Zone approach will not require an additional penalty to the final significance (alpha) level.

The performance goal was established on a systematic literature review and meta-analysis (see CIP, Section 5.6), that found the lower 95% confidence interval of the random-effects meta-analytical

estimate of the percentage achieving hemostasis at 3 min to be 65.4%, based on previous studies for hemostatic techniques used in open liver surgery. The assumption of the true rate of hemostasis at 3 minutes being 89% for GATT-Patch is based on the pre-clinical evidence and clinical judgement.

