12.3.2 TIME TO HEMOSTASIS - SAFETY POPULATION

The number of bleeding sites, mean, standard deviation, median, quartiles, minimum, and maximum time to hemostasis (seconds), including the 95% CI of the mean will be presented for Stage I and Stage II treated subjects (Safety population).

This analysis will be performed on the primary bleeding site. If there are multiple appropriate bleeding sites for one patient, the analysis will also be performed on all eligible bleeding sites that require topical hemostat application including the primary bleeding site. To account for the correlation within patient, the 95% CI will be estimated using a repeated measures linear regression model. An unstructured

covariance matrix will be used. In the event that the model fails to converge, the compound symmetry covariance matrix will be used.

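### The 95% CI for the all-bleeding-sites mean time to hemostasis comes from an unstructured-covariance model, so it may under-cover and may not contain the mean printed beside it

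*SAP*

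**What the plan says.** SAP 9.2 analyses time to hemostasis on the primary bleeding site. Where patients have several sites, it adds a second analysis: "this analysis will also be performed on all eligible bleeding sites that require topical hemostat application including the primary bleeding site". The output is a set of ordinary summary statistics: "maximum time to hemostasis (seconds) will be presented, including the 95% CI of the mean". For the multi-site case, "the 95% CI will be estimated using a repeated measures linear regression model. An unstructured covariance matrix will be used". The only alternative is conditional: "In the event that the model fails to converge, the compound symmetry covariance matrix will be used".

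SAP 12.3.2 repeats this for Stage I and Stage II patients together: "the 95% CI will be estimated using a repeated measures linear regression model", with the same covariance choice and the same fallback.

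Neither section states the mean structure, the estimation method, the degrees of freedom or the type of standard error. Neither says that the model's estimate replaces the arithmetic mean. Both sections are descriptive, and no secondary endpoint is tested.

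**The concern.** An unstructured matrix suits scheduled measurements that most subjects have. Bleeding sites are not of that kind: every treated patient has a first site, some have a second and fewer have a third. Each site order gets its own variance, and the later ones are estimated from a handful of sites. The model mean is then a variance-weighted mean, which is not the quantity printed.

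The expected data make this worse. Times are read every 30 seconds. Protocol 2.5 reports hemostasis after 30 seconds of application in preclinical tests, and the sample size assumes 89% dry at 3 minutes. A pile-up at 30 s with a thin right tail is therefore plausible. A few later sites that are nearly all at 30 s then have a very small estimated variance and take most of the weight. The model standard error treats those weights as known.

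At stake is the credibility of a descriptive interval that bears on speed of hemostasis, which Protocol 4.1 names as part of the intended benefit. With right-skewed times, the error favours the device.

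**Working it through.** **1. The plan's own figure.** The documents give no figure for this interval. The nearest one fixes the number of patients: "an evaluable sample size of 36 evaluable subjects from Stage II achieves over 90% power". With the continuity-corrected Z-test, 30/36 gives z = (0.8333 − 0.654 − 1/72)/√(0.654 × 0.346/36) = 0.1654/0.0793 = 2.09, p = 0.018, below 0.0229; 29/36 gives z = 1.74 and fails. The exact probability of at least 30/36 at a true rate of 89% is 0.906, so the stated power is reproduced. Dropout: 36/0.925 rounds up to 39 treated, and 56/0.925 to 61.

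**2. What the model estimates.** With a single mean and patient covariance Vᵢ, the estimate is Σ1′Vᵢ⁻¹yᵢ / Σ1′Vᵢ⁻¹1, with standard error (Σ1′Vᵢ⁻¹1)^(−1/2). With zero within-patient correlation, site order k has weight n_k/s_k². The printed mean instead weights every site equally.

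**3. Illustration by hand** (invented data, chosen to show the mechanism).
- First sites: 36, with 22 at 30 s, 5 at 60, 3 at 90, 2 at 150 and one each at 210, 240, 270 and 300. Mean 2550/36 = 70.8 s, SD 73.9.
- Second sites: 9, with 8 at 30 s and 1 at 60 s. Mean 300/9 = 33.3 s, SD 10.0.
- Printed mean: (2550 + 300)/45 = 63.3 s.
- Weights: 36/73.9² = 0.0066 and 9/10.0² = 0.0900. The nine second sites carry 0.0900/0.0966 = 93% of the weight, against 9/45 = 20% in the printed mean.
- Estimate: (0.0066 × 70.8 + 0.0900 × 33.3)/0.0966 = 35.9 s. SE = 1/√0.0966 = 3.22. With t(35) = 2.03, the CI is 29.4 to 42.4 s, which excludes 63.3 s.

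**4. Full REML fit of the same sites.** The result depends on which patients have the second sites. Five random pairings gave 35.6-37.1 s, with every upper limit at or below 43.4 s. One pairing with positive fitted correlation gave 28.9 s (25.1 to 32.6), centred below the shortest possible reading. That can happen because a first site in a two-site patient gets negative weight once the correlation exceeds s₂/s₁, here about 10.0/73.9 = 0.14. Compound symmetry for that pairing gave 63.5 s (42.7 to 84.4).

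With less uniform second sites (five at 30 s, two at 60, one at 90, one at 150) the printed mean is 68.0 s. Random pairings gave 62-65 s with intervals that contained it, while the positively correlated pairing gave 36.6 s (30.0 to 43.1).

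**5. Simulation of the SAP rule** (unstructured REML, compound symmetry if the fit is degenerate, t on n − 1 df). Each scenario has 200-400 data sets, times on the 30-300 s grid and the same distribution at every site order, so the true mean is known. Selected scenarios, correlation 0.2:

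| Scenario | SAP rule: coverage | SAP rule: centre / printed mean (s) | SAP rule: excludes printed mean | CS coverage | Clustered coverage |
|---|---|---|---|---|---|
| n=36, 15% with two sites, 70% dry at 30 s | 0.780 | 60.8 / 63.9 | 9.8% | 0.905 | 0.910 |
| n=36, 15%, less skewed (true mean 84.6 s) | 0.840 | 82.4 / 85.2 | 5.3% | 0.917 | 0.927 |
| n=36, 25%, 85% dry at 30 s | 0.780 | 44.8 / 46.7 | 8.7% | 0.892 | 0.880 |
| n=36, 25%, symmetric times | 0.905 | 165.3 / 165.1 | 1.3% | 0.927 | 0.953 |
| n=56, 25%, 70% dry at 30 s | 0.833 | 61.6 / 64.5 | 6.8% | 0.938 | 0.940 |
| n=150, 50%, 70% dry at 30 s | 0.925 | 64.2 / 65.0 | 0% | 0.960 | 0.955 |

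Monte Carlo error at 0.78 with 400 data sets is √(0.78 × 0.22/400) ≈ 0.02.

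Over all right-skewed scenarios with n=36 (25-85% dry at 30 s, 15-50% of patients with more than one site, correlation 0.1-0.4), the SAP rule covers 78-93%. It is 3-13% narrower than the clustered interval, sits 1-4 s below the arithmetic mean on average, and excludes that mean in 0-11% of data sets.

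**6. The alternatives on the same scenarios.** Compound symmetry covers 0.89-0.95 and excludes the printed mean in 0-1.3%. The patient-clustered interval covers 0.88-0.96 and cannot exclude the printed mean, because it is centred on it.

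**The case against.** Four points carry weight.

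- **The model is not fully specified.** The parallel logistic analyses in SAP 9.2, 12.2 and 12.3.1 use the same wording about an unstructured matrix, and there a GEE is a plausible reading. A linear GEE with one common variance and robust standard errors largely avoids the problem: coverage 0.92-0.94 and almost no exclusion. This stands as a caveat. But the SAP names no GEE and no robust standard error, and a linear model with a covariance matrix is most naturally a likelihood fit.
- **The fallback matters.** Unstructured alone covers 67-93% and excludes the printed mean in up to 22%, but that is not the SAP's rule. In the first scenario tabulated, 102 of 400 fits were degenerate and went to compound symmetry. The figures for the whole rule are the ones to use.
- **The size rests on assumptions.** The documents give no time distribution, multi-site share or correlation, and they assign no time to a 5-minute failure; SAP 7.3 rules out imputation for endpoints other than the primary. Scoring failures up to 300 s lengthens the tail that drives the pull. With symmetric times there was no pull, though coverage was still about 0.905.
- **The consequence is small.** The primary-site analysis has one observation per patient. The all-sites version is supplementary, nothing is tested on it, and the printed mean, median and quartiles do not change. This stands, and it sets the priority.

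A reader might infer from the hand example that the reported interval will exclude its own mean. The documents do not support that: the example uses nearly uniform second sites, and exclusion was the exception in every simulated scenario.

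**Conclusion.** The point holds as a conditional one. Followed as written and read as an intercept-only likelihood model, the rule attaches to the printed all-sites mean an interval for a differently weighted mean. With right-skewed times and few later sites, that interval tends to be too narrow and centred low. Under the assumed inputs (36-39 patients, about 5-18 with more than one site, correlation 0.1-0.4, failures scored up to 300 s), coverage is roughly 78-93% instead of 95%, the centre is about 1-4 s low on average, and the printed mean is excluded in about 0-11% of trials.

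The increase to 56 evaluable patients does not remove it (coverage 0.83 in the scenario run). The effect is mild with less skewed times and largely fades at 150 patients.

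A reader might also infer that the time-to-hemostasis endpoint as a whole, or the trial's conclusion, is compromised. It is not: the primary-bleeding-site analysis and the primary test do not use this model. This is a lower-priority correction to a descriptive interval.

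**What to change.** In SAP 9.2 and 12.3.2, compute the all-sites CI around the printed mean ȳ with a patient-clustered (sandwich) standard error, SE² = [n/(n−1)] Σᵢ(Σⱼ(yᵢⱼ − ȳ))² / N², for n patients and N sites, and t on n − 1 degrees of freedom. A bootstrap that resamples patients would also serve. If a model is kept, make compound symmetry (a random patient intercept) the first choice rather than the fallback, and print the model mean next to its CI. State how a 5-minute failure enters the mean. Leave the primary-bleeding-site analysis as it is.

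The cost is a wording change in two sections and a few lines of code. The interval will be slightly wider. Coverage of the replacement can still fall somewhat below 95% with extreme pile-up at 30 s (0.88 in the worst scenario run), but the interval will belong to the mean it accompanies.
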